13.3 Data Entry

Data entry for all self-report measures will be completed directly by the participant onto a tablet computer using the ACASI software. Data from the two additional sources urine and hair data, and EMR data are entered into Excel spreadsheets at the PI's lab.

All non-ACASI data are entered by two research assistants separately into identical, pre-formatted Excel spreadsheets. The Project Coordinator then combines the entries

and uses a simple, pre-formatted row of subtraction cells to verify that all entries are identical (yielding a value of zero). Any non-zero values trigger analysis of the source data to resolve the discrepancy.

Regarding the ACASI: the accuracy with which data input matches data output will be exhaustively checked prior to beginning the trial, using sample protocols. (Note: we have never found data coding errors on the part of the software in all previous trials.) Further, we will test a randomly chosen sample protocol monthly following trial initiation. Although no problems are expected given past experiences with this technology, any evidence of errors in data recording by the ACASI will result in dropping all participants since the last quality check. In addition, data will be checked once per month for out of range values and other quality issues. All data will be accessible only with appropriate passwords known only to the PI and project coordinator.

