Objectives:	Primary: Co-primary outcomes will include confirmed 7- and 90-day period-prevalence abstinence, and days of marijuana use in the past 90 days. All primary outcomes will be based on participant report during the postpartum timeline follow-back interview; the 7- and 90-day dichotomous abstinence measures will be confirmed using results from urine and hair toxicological analysis, respectively. Evidence of use from either the timeline follow-back interview or toxicological testing will result in that participant being considered non-abstinent.
	Secondary: Secondary outcomes will include (a) birth outcomes from the Electronic Medical Record (EMR), including birth weight, length of hospitalization, and days in Neonatal Intensive Care; (b) help-seeking, particularly engagement in treatment services for marijuana use; (c) comparisons of the three intervention configurations (SBIRT only, texting only, or combined) to each other, rather than to the control condition; and (d) comparison of time-control and screen-only control participants.
Population:	Participants will be pregnant women age 18 to 40, 20 weeks or less gestation, seeking care at the WSU UPG or Thea Bowman prenatal care clinics.
Number of Sites:	Wayne State University
Description of Intervention:	This R34 clinical trial planning grant proposes the development and preliminary validation of two high-reach and mutually compatible technology-based interventions for marijuana use during pregnancy: an interactive computer-delivered brief intervention, and a tailored text messaging intervention.
Study Duration:	21 months
Subject Participation Duration:	20 – 36 weeks (From prenatal appointment before 20 weeks gestation until follow-up postpartum)
Estimated Time to Complete Enrollment:	21 months

Schematic of Study Design:

NIDA Program	[name]
Official:	[contact]; [contact] (fax)
	[contact]
Institutions:	Wayne State University
Other Key	[name]
Personnei:	Wayne State University
	[name].
	Wayne State University

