2 OBJECTIVES

2.1 Study Objectives/Outcome Measures

2.1.1 Primary

Co-primary outcomes will include confirmed 7- and 90-day period-prevalence abstinence, and days of marijuana use in the past 90 days. All primary outcomes will be based on participant report during the postpartum timeline follow-back interview; the 7and 90-day dichotomous abstinence measures will be confirmed using results from urine and hair toxicological analysis, respectively. Evidence of use from either the timeline follow-back interview or toxicological testing will result in that participant being considered non-abstinent.

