5.2 Enrollment/Baseline

Participants meeting all eligibility criteria will be offered participation in the pilot clinical trial. Those providing written informed consent will again be given the Tablet PC and headphones. Participants will then be randomized to one of the five conditions by the CIAS software. Total time spent for each participant will be approximately 10-30 minutes, depending on condition, with the exception of those in the screen only condition (who will be done sconer). Randomization will be stratified on race, age, and frequency of marijuana use prior to pregnancy. This study will include five conditions with an *n* of 20 per intervention condition (e-SBIRT only, texting only, or combined) and 10 per control condition (assessment only or screen only). This reduced *n* for the control conditions will simultaneously allow us to (a) focus analyses on feasibility and acceptability, given that 75% of participants will receive one or more interventions; (b) obtain a full control group for primary analyses, at minimal additional cost/effort, by collapsing the two control conditions (if they—as expected—do not differ significantly from each other); and (c) pilot the addition of a screen-only control group in order to identify any practical or procedural challenges prior to a future Stage II trial.

Table 1. Study arms and associated components

Condition	Screening	Assessment battery	Text preferences	eSBIRT	Tailored texting
1. Screen only control	х				
2. Assessment control	х	х			
3. eSBIRT only	х	х		х	
4. Tailored text only	х	х	х		х
5. eSBIRT + Tailored text	x	x	x	х	х

After determining eligibility by the previously mentioned screening procedures and having the participant indicate interest in continuing, the RA reads through the Trial consent form.

OK great. Here's a form describing this second study in detail. Let's go over it together. If you decide you want to participant in this study you will need to sign 2 copies of this form. You will keep one copy and one copy will be kept in a locked file cabinet at WSU in [name] office.

Allow the participant time to read, review, and ask questions. Once all questions are answered participant must sign 2 copies of the form and answer the quiz to determine they understand the study.

Consent Quiz

1.	Is your participation voluntary?	Correct answers _ Yes

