13.2 Data Capture Methods

Most data will be collected using computer-based self-interview (ACASI) technology on a Tablet computer, with data being encrypted in transit and stored on a secure server; further, all data in the ACASI system will only be identified only with a non-identifying ID number for the participant. A single paper copy of the table linking this number to the participant's name will be kept locked in a file cabinet in the PI's lab, with a password protected electronic version stored on a secure WSU server with restricted access, such that only the PI and the Project Coordinator will have access to the server and to the passwords for the linking table file. The PI's lab is kept locked, in a locked and alarmed secure building on campus.

Three additional sources of data will not be collected directly from the participant using the ACASI system. First, data will also be obtained from hair and urine testing performed at follow-up. These samples will also be identified only using the non-identifying participant ID number; the commercial labs doing testing the samples will never obtain identifying information on any participant. Further, data from this testing will not be available until after the participant has been discharged from the hospital, further limiting the potential for any negative consequences relating to prenatal drug exposure. Second, data will be obtained by DMC clinic staff from the neonate's electronic medical record (EMR). We will provide this staff person—who will already have access to clinic medical records—with the participant's name and date of birth, the infant's name and date of birth, and other information as needed so that she can accurately identify the infant in question. She will record birth weight, length of stay, and number of days in neonatal intensive care (if any) on a paper form containing only the participant ID number.

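### As written, any ACASI recording error drops every participant since the last monthly check, including outcome data collected outside the ACASI

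*Combined protocol and SAP*

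**What the plan says.** Section 13.3 (Data Entry) provides a monthly test of a randomly chosen sample protocol and a monthly check for out-of-range values. It then says that "any evidence of errors in data recording by the ACASI will result in dropping all participants since the last quality check". Section 11 repeats the rule in the same terms. The trigger has no materiality threshold, the unit removed is the participant, and the meaning of dropping is not defined.

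Section 13.3 also reports that "we have never found data coding errors on the part of the software in all previous trials".

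Other data reach the trial by a different route. Under section 13.2, "data will also be obtained from hair and urine testing performed at follow-up", and a clinic staff member extracts birth outcomes from the medical record: "She will record birth weight, length of stay, and number of days in neonatal intensive care (if any) on a paper form". Section 13.3 adds that "All non-ACASI data are entered by two research assistants separately into identical, pre-formatted Excel spreadsheets", with discrepancies resolved against source and nobody dropped.

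Section 2.1.1 lets a positive test decide the abstinence outcome by itself: "Evidence of use from either the timeline follow-back interview or toxicological testing will result in that participant being considered non-abstinent".

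Section 9.1 allows multiple imputation where appropriate. Nothing in section 9 says that all randomised women are analysed, or what happens to women removed under this rule.

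**The concern.** The rule removes people when the fault lies in records. Three kinds of sound data would go with a dropped woman:

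- Birth weight, length of stay and neonatal intensive care days, which are secondary outcomes taken from the medical record onto paper.
- Urine and hair results. A positive result alone settles non-abstinence, whatever happened to the tablet data.
- Sessions outside the window. A woman enrolled in a faulty month has her follow-up 20 to 36 weeks later, and a woman whose follow-up falls in a faulty month may have a sound baseline.

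At stake is avoidable loss of randomised women from groups of 20 (two control subgroups of 10), under a rule whose scope is left to be settled after an error has been found.

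**Working it through.** The plan gives no figure for the size of this loss, so there is none to reproduce. The scale can be worked out from its inputs.

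**Inputs.** 80 women in four groups of 20 (sections 1.1 and 3.3.1). The Protocol Summary gives 21 months both for study duration and for completing enrolment, and 20 to 36 weeks' participation, described as "From prenatal appointment before 20 weeks gestation until follow-up postpartum". Checks are monthly (section 13.3). Assumptions: even accrual, all 80 followed up, dropped women not replaced, losses spread evenly over the four groups, 4.348 weeks per month.

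**Women per window, enrolments only.** 80 / 21 = 3.81, and 3.81 / 80 = 4.8%. Chance variation (Poisson, 95%) gives 1 to 8.

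**Women per window, enrolments and follow-ups.** Each woman has two sessions at least 20 / 4.348 = 4.6 months apart, so both cannot fall in one monthly window and sessions can be counted as women. 160 / 21 = 7.62, and 7.62 / 80 = 9.5%; Poisson range 3 to 13. If the 21 months cover the whole trial, 7.6 is the average per month. If enrolment alone takes 21 months, 7.6 is the rate while both kinds of session run, and months with only one kind stay at 3.8.

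**Effect on precision.** The relative increase in the standard error of a two-group comparison is sqrt(20 / n) - 1, where n is the remaining group size.

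| Women lost | n per group | Increase in standard error |
|---|---|---|
| 3.81 | (80 - 3.81) / 4 = 19.05 | 2.5% |
| 7.62 | (80 - 7.62) / 4 = 18.10 | 5.1% |

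**Shorter accrual.** If the 21 months include follow-up, the delay of 4.6 to 8.3 months (36 / 4.348 = 8.3) leaves 16.4 to 12.7 months for enrolment. Enrolments per month become 80 / 16.4 = 4.9 to 80 / 12.7 = 6.3. With follow-ups the count doubles to 9.8 to 12.6, but only while both run: 16.4 - 4.6 = 11.8 months, or 12.7 - 8.3 = 4.4 months. Over the whole 21 months the average is still 160 / 21 = 7.6.

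**The case against.** The strongest reply is that the rule was never meant to reach beyond ACASI records. In section 13.3 its paragraph opens by limiting itself to the ACASI and follows a separate paragraph on non-ACASI data. In section 11 the neighbouring sentences concern software accuracy. Both are data-quality sections, while section 9 governs analysis and defines no such exclusion. This is a fair reading and may be the intended one. But neither section states it, and the object of the verb in both is the participant.

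The event is also hypothetical, and this is a pilot that section 9.2 does not expect to be adequately powered. Both points stand and keep the priority low. A mechanical rule has some merit too, since it leaves no discretion; the fix has to preserve that.

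Readers might infer more than the documents support:

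- *That the rule biases the comparison between arms.* A calendar window takes no account of arm, and no differential loss is shown.
- *That exclusions could be steered.* The principal investigator and coordinator can see allocation (section 3.3.2), and the investigator part-owns the software company (section 8). That is a reason to settle the rule in advance; nothing shows that it has been or would be misused.
- *That a trigger typically costs 10 to 13 women.* Those counts are peaks confined to the months of overlap.
- *That errors are to be expected*, because section 4.3 mentions software issues that were easily fixed. It does not say these were recording errors.

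**Conclusion.** The point holds in a limited form. Followed literally, sections 11 and 13.3 impose a post-randomisation exclusion that throws away sound laboratory, medical-record and out-of-window data, and section 9 does not reverse it. The average cost per trigger is modest: about 3.8 to 7.6 women, or 2.5% to 5.1% on the standard error. It is nil if no error is found. These figures rest on even accrual, complete follow-up and no replacement. On replacement the documents are silent, although staff monitor randomisation to reach 20 per condition (section 3.3.1). The loss is avoidable by clearer wording and is not a threat to the trial.

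**What to change.** Reword sections 11 and 13.3 along these lines:

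- If an ACASI recording error is found, the affected ACASI fields recorded since the last check are set to missing. If they cannot be identified, all ACASI data recorded in that window are set to missing.
- A named person without access to allocation makes that decision. Given section 3.3.2, this cannot be the principal investigator or the coordinator.
- Every randomised woman stays in her randomised group with her laboratory, medical-record and unaffected ACASI data.
- Missing outcomes and missing baseline covariates are handled by the multiple imputation planned in section 9.1, with arm and toxicology results in the model. Baseline frequency of use must be covered, because sections 9.3's abstinence and days-of-use models both adjust for it. Section 5.2 says "Randomization will be stratified on race, age, and frequency of marijuana use prior to pregnancy", so frequency should also be held for screen-only controls, who have no baseline battery.
- Outcomes settled only by a positive test are not analysed alone. Keeping positives while test-negative women go missing would understate abstinence. That hazard belongs to a careless version of this fix, not to the present plan.
- Dropping all participants in the window is kept as a sensitivity analysis.

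The cost is wording in two sections and, if an error occurs, slightly more data-management and imputation work. The gain has a limit. When the timeline follow-back itself is affected, little is recovered for days of use, or for abstinence in test-negative women; what is saved is mainly positive tests and birth outcomes.

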13.4 Schedule and Content of Reports

PI, the project manager, and the RA will meet at least monthly while data collection is ongoing, to review all data collection procedures, as well as recent data, to ensure that study procedures are being followed appropriately and all data are present.

13.5 Stud y Records Retention

Study records will be maintained for at least three years from the date that the grant federal financial report (FFR) is submitted to the NIH.

13.6 Protocol Deviations

A protocol deviation is any noncompliance with the clinical study protocol, Good Clinical Practice, or Manual of Procedures requirements. The noncompliance may be on the part of the subject, the investigator, or study staff. As a result of deviations, corrective actions are to be developed by the study staff and implemented promptly.

These practices are consistent with investigator and sponsor obligations in ICH E6:

- Compliance with Protocol, Sections 4.5.1, 4.5.2, 4.5.3, and 4.5.4.
- Quality Assurance and Quality Control, Section 5.1.1
- Noncompliance, Sections 5.20.1 and 5.20.2.

All deviations from the protocol must be addressed in study subject source documents and promptly reported to NIDA and the local IRB, according to their requirements.

14 PUBLICATION/DATA SHARING POLICY

This study will comply with the *NIH Public Access Policy*, which ensures that the public has access to the published results of NIH funded research. It requires scientists to submit final peer-reviewed journal manuscripts that arise from NIH funds to the digital archive PubMed Central upon acceptance for publication.

This study also follows the policy that requires that all clinical trials be registered in a public trials registry such as *ClinicalTrials.gov*, which is sponsored by the National Library of Medicine. The Clinical Trials registration number for this study is **NCT02191605**.

